Background	Because of an increased risk of major, non-major, and intracranial bleeding and an uncertain effect on survival and post-thrombotic complications, thrombolysis is not routinely recommended in the guidelines for intermediate- risk patients. However, studies have evaluated half-dose (50 mg dose) tissue plasminogen activator (tPA) and this appears to be effective for treating PE with a reduced yet still significant risk of bleeding. Catheter-directed thrombolysis studies have used even lower dose tPA (24mg) with significant reduction in clot burden, right ventricle to left ventricle ratios, and less bleeding; however, catheter-directed therapy requires a procedure which is time consuming, costly, center dependent, and introduces other potential complications. Based on our extensive clinical experience in treating acute PE, we believe that even lower doses of systemic (intravenous) tPA may be effective and safe, as well as simpler and more accessible than any form of catheter-directed thrombolysis (CDT). In addition, usage of the direct oral anticoagulant (DOAC), apixaban, after completion of anticoagulation therapy for PE has been shown to be effective in preventing recurrent VTE in patients while having a very low risk of major bleeding.
	To understand ways to improve PE patient outcomes while reducing risk of major bleeding, our proposed trial will compare a baseline CTA to a 24 hour CTA after administration of a 24 mg dose of systemic, (intravenous) tPA (treatment A) for intermediate-high risk PE patients. As a secondary endpoint we will compare treatment A to conventional anticoagulant therapy (treatment B). Patients with a low risk of bleeding will then receive standard dose apixaban. In addition to our primary endpoint analysis, we will follow patients after discharge to evaluate long-term efficacy and safety of the thrombolytic therapy on endpoints such as right ventricular (RV) function, residual clot burden, and long-term mortality.
Diagnosis and Main	
Criterion for Inclusion	Adult individuals with intermediate-high risk (submassive) PE.
Primary Study Objective	To determine whether very low 24 mg dose systemic thrombolytic therapy is effective and safe in treating intermediate-high risk PE compared to anticoagulation alone.

Primary Endpoint	Mean change in percentage of Refined Modified Miller Score (RMMS) (measurement of extent of clot lysis) between baseline CTA and 24 hour CTA after 24 mg of systemic (intravenous; IV) tPA.
Primary Hypothesis	Very low-dose intravenous tissue-type plasminogen activator (24 mg) + standard anticoagulation therapy (intravenous heparin) for treatment of acute PE in intermediate risk patients will have clot lysis of at least 15% by chest CTA at 24 \pm 6 hours post infusion compared with baseline CTA. All patients will be treated with oral apixaban at the approved dose of 10 mg twice-daily starting at least 24 hours after completion of the IV study drug for seven days followed by 5 mg twice-daily for at least 6 months, with the potentiality of decreasing the apixaban dose again to 2.5 mg twice-daily after 6 months.
	This is a randomized, double-blinded, placebo-controlled, single-center study intended to investigate very low dose systemic (IV) tPA along with standard anticoagulation therapy as a treatment for intermediate-high risk (submassive) PE. The study is planned to evaluate the reduction in clot burden based on the obstruction index using the Refined Modified Miller Score (RMMS), improvement in right ventricular (RV) function, and overall safety in the two treatment groups. Subjects with intermediate-high risk PE (hemodynamically stable PE with significant clot burden a RV dysfunction an at least one elevated biomarkers,will be randomized to one of two treatment groups: 24mg of systemic (IV) tPA + IV unfractionated heparin versus saline placebo + IV unfractionated heparin.
	Approximately 40 subjects will be enrolled. These subjects will be randomized in a 1:1 ratio (approximately 20 per treatment arm) to receive 24 mg tPA [Activase (alteplase)] + standard anticoagulation therapy (intravenous heparin) vs placebo + standard anticoagulation (intravenous heparin) therapy.
Study Design and Methodology	Upon enrollment, the standard of care labwork, chest contrast-enhanced computed tomographic angiogram (chest CTA), echocardiogram and duplex ultrasound of lower extremities will be reviewed The sPESI core will be calculated.
	After delivery of the systemic (IV) tPA/placebo, patients will continue IV unfractionated heparin therapy for at least 24 hours. If there is no evidence of active bleeding nor significant hemoglobin drop (i.e., $\geq 2 \text{ mg/dL}$), patients will be transitioned to standard dose apixaban, 10 mg twice-daily x one week followed by 5 mg twice-daily for at least 6 months. Some patients will require indefinite apixaban therapy based on patient-specific factors, including unprovoked nature of PE event, and/or persisting DVT/PE risk factors. Finally, consideration will be given for decreasing the apixaban dose to 2.5 mg twice-daily after 6 months. Apixaban was selected as the anticoagulant of choice due to its very favorable bleeding profile in large clinical trials, which is an important consideration when prescribing an anticoagulant following systemic thrombolysis.
	Within 24 \pm 8 hours post study drug infusion, a repeat chest CTA and echocardiogram will be performed. sPESI will also be calculated at this timepoint.

٦

	At Day 30, 180 and 365, all subjects will have clinic visits which will include a physical exam, repeat echocardiogram (at Day 30 & 180), 6 minute walk test (6MWT), quality of life questionnaires, assessment of adverse and bleeding events and a review of concomitant medications including compliance with apixaban. At Day 3, 7, 90 and 270, a remote health check will occur via telephone or email assessing adverse and bleeding events, alongside a review of concomitant medications (including an assessment of compliance with apixaban).
	If any subject experiences an adverse event (AE), the investigator may, at his or her discretion, decrease or discontinue the study drug or apixaban.
	The DMC will meet after 10 subjects are enrolled; bleeding and other complications will be reviewed. An interim analysis will occur after 20 subjects have completed Day 30. The DMC will meet again after 30 subjects have completed Day 30. Because it is a single-center study, the investigators and study coordinators will be acutely aware of all adverse events.
	The primary analyses will compare the clot lysis on CTA in treatment A at 24 hours post study drug infusion. See Section 7 for a complete discussion of the statistical analysis.
Inclusion Criteria	 Male or female 18-75 years in age Chest CT angiogram evidence of proximal PE with a filling defect in at least one main pulmonary artery or lobar artery PE symptom duration ≤14 days Intermediate-high risk PE: significant clot buden with RV dysfunction, an elevation in troponin > 0.05 ng/mL and/or brain natriuretic peptide (BNP) > 100 pg/mL, and hemodynamically stable (systolic blood pessure>90mm Hg without the use of vasopressor support) Randomization within 36 hours of anticoagulation Signed and dated informed consent obtained from subject or legally authorized representative before initiation of any study procedures
Exclusion Criteria	 Stroke or transient ischemic attack (TIA), head trauma, or other active intracranial or intraspinal disease within one year Recent (within one month) or active bleeding from a major organ Major surgery within 14 days Clinician deems the subject too high-risk for bleeding using HAS-BLED criteria. History of any hematologic disease or coagulopathy Cirrhosis (as determined by Child-Pugh B or C) History of heparin-induced thrombocytopenia (HIT) Hemodynamic instability defined as systolic blood pressure (SBP) less than 90 mm Hg and/or use of vasopressors for greater than 15 minutes Severe hypertension as define as systolic blood pressure (SBP) greater than 180 mm Hg Cardiac arrest or active cardiopulmonary resuscitation (CPR) Receiving neuraxial anesthesia or undergoing spinal puncture

Γ

	 Patient with prosthetic heart valves Evidence of irreversible neurological compromise Evidence of poor functional status History of major gastrointestinal bleed within the last month Active gastric or duodenal ulcers Use of thrombolytics or glycoprotein IIb/IIIa antagonists within 3 days prior to diagnosis Lovenox administration within 12 hours of randomization Direct-acting oral anticoagulant use (dabigatran, rivaroxaban, apixaban, or edoxaban) with last known dose within 48 hours Hemoglobin < 10 g/dL
	 creatinine clearance < 30 mL/min platelets < 100 thousand/µL INR > 1.4 Alanine transaminase (ALT) or aspartate transaminase (AST) ≥ 2 times upper limit of normal (ULN) Total bilirubin (TBL) ≥ 1.5 times ULN (except due to confirmed Gilbert's syndrome) Patient is pregnant (positive pregnancy test; women of childbearing capacity must be tested prior to enrollment) or breast feeding Patient who is a prisoner, or if subject who becomes compulsory detained Active cancer defined as diagnosis of cancer within six months before the study inclusion, or receiving treatment for cancer at the time of inclusion or any treatment for cancer during 6 months prior to randomization, or recurrent locally advanced or metastatic cancer. Known allergy, hypersensitivity or thrombocytopenia from heparin, tPA, or apixaban or iodinated contrast except for mild-moderate contrast allergies for which steroid pre-medication can be administered within 12 hours prior to the CTA. HIV/AIDS Weight >130 kg or < 40 kg on day of randomization
Sample Size	In this trial, 40 subjects (20 per arm) will be randomized into two treatment arms, 1) 24 mg IV PA + standard anticoagulation therapy (IV heparin) vs 2) saline placebo + standard anticoagulation therapy (IV heparin), using a computer program at Cedars-Sinai Medical Center in Los Angeles, California. Additional subjects may be consented to compensate for screening failures and/or treated patients who lack sufficient data. Approximately 40 subjects will be enrolled into the study, with approximately 20 subjects in each arm. A subject will be deemed evaluable if he/she has valid CTA imaging evaluations at both baseline and $\leq 24h \pm 8$ hours post-end of infusion and successfully completed administration of study drug infusion. Randomized subjects who do not complete blinded study drug administration (i.e., subjects who stop the IV infusion early due to AEs) will still be followed for safety through Day 30.

	The planned sample size is based on a two-sided two-sample equal-variance t-test. A previous study [19] showed that the mean and standard deviation of percentage change in RV/LV ratio from baseline to 48 hours are 26 and 22.7, respectively. Assuming these hold for our study , data from 17 patients per group (34 total) achieve 90% power to detect a mean difference of 26 percentage units between the two treatments with 5% significance level using a two-sided two-sample equal-variance t-test.

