5.2.1. SCREENING ASSESSMENTS

The following assessments will be performed at Screening:

- Informed consent
- Medical history and demographics
- Inclusion/exclusion criteria
- Pregnancy test if the subject is female and of child-bearing potential.
- Vital signs and physical exam including blood pressure, respiratory rate, heart rate, and SpO2.
- Electrocardiogram (ECG; 12 lead)
- CT Angiogram to evaluate the anatomic location of PE (at least pulmonary or lobar artery involvement). The RV/LV ratio at end-diastole and the initial Refined Modified Miller obstruction index score will be determined from this image by a third party blinded radiologist.
- Echocardiogram to measure: RV dysfunction, RV/LV ratio, TAPSE, estimated RVSP, and collapse of the IVC with respiration.
- Laboratory testing including hemoglobin (Hgb), hematocrit (Hct), platelet count, blood urea nitrogen (BUN), creatinine, aPTT, PT and INR, liver function tests (ALP, ALT, AST), troponin I, and B-type natriuretic peptide and (BNP).
- Simplified Pulmonary Embolism Severity Index (sPESI) score calculation
- Lower extremity duplex ultrasound

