6.2.1. DATA FORMS AND DATA ENTRY

Data will be collected via case report forms (CRF) and entered into a research database maintained in REDCap (Research Electronic Data Capture). This data will be electronically verified through use of programmed edit checks specified by the clinical team. Discrepancies in the data will be flagged in REDCap and corrected by the study team. An audit trail within REDCap will track all changes made to the data.

CT and Echo DICOM images will be transmitted to the imaging core laboratory, Syntactx. A central reader will review the images and complete a case report form. Syntactx will read the images in bulk at the end of the study.

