7.1.3. ATTRITION

The determined sample size is 17 subjects per arm (34 total), but we will enroll 20 per arm (40 total) to allow for potential attrition.

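### Open-ended replacement of treated patients without usable data duplicates the attrition allowance and hides losses from an evaluable set defined by events after randomisation

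*Combined protocol and SAP*

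**What the plan says.** The synopsis (Sample Size) and section 3.2 carry the same sentence: "Additional subjects may be consented to compensate for screening failures and/or treated patients who lack sufficient data". Neither gives a limit, says who decides, or defines how much data is enough.

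Section 7.1.3 sets the requirement at 17 per arm and adds: "we will enroll 20 per arm (40 total) to allow for potential attrition". No attrition rate is stated.

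The synopsis defines evaluability in two parts. On scans: "A subject will be deemed evaluable if he/she has valid CTA imaging evaluations at both baseline and" about 24 hours after infusion. On exposure, the patient must have "successfully completed administration of study drug infusion". Patients who stop the infusion early because of adverse events stay in safety follow-up, through Day 30 according to the synopsis and for the remainder of the study according to section 3.5.

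Section 3.5 ends the alteplase infusion for, among other things, a related serious adverse event, new neurological symptoms, new severe headache or life-threatening bleeding. Section 6.3.2 stops it if bleeding occurs.

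On reading the scans, section 6.2.1 states: "Syntactx will read the images in bulk at the end of the study". Section 5.2.1 lists among the screening assessments that the "initial Refined Modified Miller obstruction index score will be determined from this image by a third party blinded radiologist".

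The statistical text (synopsis and section 7.1.1) names no intention-to-treat population, gives no rule for a missing 24-hour RMMS, and does not say how patients who have been compensated for enter the analysis.

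**The concern.** A treated patient without a usable 24-hour scan, or with an interrupted infusion, is not a random loss. The protocol's own stopping reasons link an incomplete infusion to bleeding and other adverse events, and a patient who has died or become unstable may not be scanned. An efficacy set built on these conditions selects patients partly on what happened after treatment.

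This matters because the primary hypothesis sets a threshold, at least 15% lysis in the tPA arm, and a few patients in an arm of 20 can move the mean across it. Topping up with further patients does nothing about that selection. It presents a full complement of scanned patients, so the loss is harder to see. It also leaves the number randomised without a fixed end and gives tPA to patients whom the power calculation does not need.

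**Working it through.** **Inputs.** From section 7.1.1: baseline RMMS 21.14 units; 15% of this is 0.15 × 21.14 = 3.171 units; SD of the change 2.7 units; two-sided α = 0.05. RV/LV comparison: difference 26, SD 22.7. From section 7.1.3: 17 per arm required, 20 enrolled.

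**Step 1. Reproduce the stated power at 17 per arm** (t-test, noncentral t).
- RV/LV, A vs B: noncentrality (26/22.7) × √(17/2) = 3.34 on 32 df. Power is 89.9%; stated 90%.
- RMMS, A vs B: (3.171/2.7) × √(17/2) = 3.42 on 32 df. Power is 91.3%; stated 91%.
- RMMS within A: (3.171/2.7) × √17 = 4.84 on 16 df. Power is 99.5%, as stated. This figure needs a paired test, not the two-sample test named in the text.

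**Step 2. What the allowance already covers.** 17/(1 − 0.15) = 20, so 3 losses per arm (15%) still leave 17.

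**Step 3. Power without replacement.**

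| Evaluable per arm | RV/LV, A vs B | RMMS, A vs B | RMMS within A (paired) |
|---|---|---|---|
| 20 (no loss) | 94.2% | 95.1% | 99.9% |
| 17 (15% loss) | 89.9% | 91.3% | 99.5% |
| 14 (30% loss) | 83.1% | 84.9% | 98.2% |

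**Step 4. Where a bias would come from.** The documents give no rate of missing scans, so the losses here are assumed. Suppose scanned tPA patients average 15% lysis and k unscanned patients have none. The mean over all treated patients is 15 × (20 − k)/20 without replacement, and 15 × 20/(20 + k) if the arm is topped up to 20 scanned.

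| k unscanned | All treated, no replacement | All treated, topped up | Evaluable-only result |
|---|---|---|---|
| 1 | 14.25% | 14.29% | 15% |
| 2 | 13.5% | 13.64% | 15% |
| 3 | 12.75% | 13.04% | 15% |

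The gap to 15% is almost the same in both middle columns. It arises from leaving out unscanned patients, not from replacing them. Under the harsher assumption that unscanned patients worsened by 3.171 units, k = 3 gives 10.5% without replacement and 11.1% with it; the evaluable-only result again reads 15%.

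**Step 5. Extra exposure.** The plan does not say what number the top-up aims for. If it were 20 evaluable per arm, 20/(1 − q), rounded up, gives 22, 23 or 24 randomised per arm for assumed non-evaluable rates q of 5%, 10% or 15%. That is 2 to 4 more patients given tPA.

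**Step 6. Timing.** A scan that was never done is known the same day. Only the core laboratory's view of whether a completed scan is readable waits until the end of the study. Replacement for an unreadable scan during enrolment would therefore rest on a site judgement that the plan does not define.

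**The case against.** A reader might infer that patients too ill to be scanned are swapped for scannable ones and that replacement itself pushes the lysis estimate upward. The documents do not support this. The wording is permissive. Added subjects are randomised 1:1 in permuted blocks (section 5.3.1), so they do not take the lost patient's place within an arm. Nothing removes the lost patient from the report: safety follow-up continues, section 6.1.2 keeps data collected before withdrawal, and deaths, severe bleeding and decompensation are safety endpoints in their own right. Step 4 shows that the estimate is the same with or without replacement.

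Nor does the end-of-study reading make replacement unworkable, since an absent scan is visible at once and the baseline score is listed as a screening assessment.

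The losses may also be small. Section 7.1.2 expects bleeding in 5% or less by Day 30, which is one patient in 20; the tenecteplase trial cited in section 1.1 had 30-day mortality of 2.4% and 3.2%; entry requires haemodynamic stability; and the infusion lasts about 20 minutes. One loss costs 0.75 points. A bleed does not show that the clot failed to lyse, so scoring it as no lysis is an assumption, and for A versus B the direction of any bias is unknown. All of this stands.

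Two further arguments carry less weight. The first is that 40 is stated as the number to be randomised; but an uncapped provision beside it leaves that number open. The second is that 20 per arm does not guarantee 17: with non-evaluable rates of 5%, 10% and 15%, the chance that both arms keep at least 17 is 97%, 75% and 42%. That is correct, but falling short costs little power, as the 14-per-arm row shows.

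**Conclusion.** The point holds as a modest improvement that costs little. Replacement of treated patients is permitted without limit, on top of an allowance that already covers 15% loss. Its effects are on visibility, the fixed sample size and tPA exposure.

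The possible bias belongs to the evaluable-only rule. On the assumed losses of 1 to 3 of 20 with no lysis, it is 0.75 to 2.25 percentage points against a 15% threshold. That rests on three assumptions: scanned patients average exactly 15%, unscanned patients have zero lysis, and the primary analysis uses the evaluable set. The plan implies the last of these but does not say so. A claim that replacement inflates the result, or that deleting it would correct the estimate, goes beyond the documents.

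**What to change.** - In the synopsis and section 3.2, delete the half of the sentence that concerns treated patients. Fix randomisation at 40 and allow extra consents only for subjects never randomised.
- Include in the primary RMMS analysis every randomised, treated patient with both CTAs, whether or not the infusion was completed.
- Report missing 24-hour CTAs by arm with the reason.
- Add one sensitivity analysis, applied to both arms, that scores CTAs missing through death, bleeding or instability as no lysis (24-hour RMMS set equal to baseline). Label it as a conservative assumption.
- Reconcile the synopsis and section 3.5 on how long patients who stop the infusion early are followed.

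The cost is one clause removed in two places, a sentence defining the analysis set, one table of reasons and one sensitivity analysis. The downside is power if losses are heavy. Up to 3 per arm keeps the stated 91% (RMMS, A vs B) and 90% (RV/LV). With 6 per arm lost, twice the allowance, these fall to about 85% and 83%.

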1.2.1. PRIMARY ENDPOINT

Change in percentage of clot lysis by chest computed tomographic angiography (chest CTA) (Refined Modified Miller Score; RMMS) after 24 mg of systemic (intravenous; IV) tPA compared with baseline CTA RMMS.

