1.2.2. SECONDARY ENDPOINTS

- Change in percentage of clot lysis by chest computed tomographic angiography (chest CTA) (Refined Modified Miller Score; RMMS) from baseline to 24 hours for treatment A compared with treatment B.
- Change in right ventricular to left ventricular diameter ratio (RV/LV) as measured by chest CTA from baseline to 24 ± 8 hours after the infusion of very low dose systemic (IV) tPA in patients with acute intermediate-high risk (submassive) PE compared with placebo.

- Change from baseline in echocardiographic parameters including RV/LV ratio, tricuspid annular plane systolic excursion (TAPSE), estimated right ventricular systolic pressure (RVSP), and collapse of the inferior vena cava (IVC) with respiration within 24 hours ± 8 hours and at 30 ±5 days after the end of the systemic (IV) tPA infusion compared with placebo.
- 6 Minute Walk Test (6MWT) distance with the Borg Dyspnea Scale score (Borg score) and requirement for oxygen therapy at Day 30, 180 and Day 365 clinic follow-up compared with placebo.
- Quality of life (QOL) as measured by the PROMIS PF-6 and Pulmonary Embolism Quality of Life (PEmb-QOL) at Day 30, 180, and 365 clinic follow-up compared with placebo.
- Recurrent DVT and PE at Day 30, 180 and 365 compared with placebo. Since all patients will be on apixaban, we will compare DVT and PE recurrence rates with historic controls.

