3.5. DISCONTINUATION OF SUBJECTS FROM TREATMENT

Discontinuation of alteplase

If a subject develops the following adverse events the alteplase infusion will be permanently discontinued:

- SAE or other safety concern that is related to study drug treatment
- New onset of neurological symptoms
- New onset of severe headache
- Major life-threatening bleeding (per GUSTO criteria)
- Initiating or continuing study drug places the subject at undue hazard as determined by the Investigator

The subject will continue to be followed for the remainder of the study. The subject will be assessed immediately after the infusion and appropriate clinical treatment will be instituted.

One of the PIs will use his clinical judgment to determine the treatment needed and this may include imaging studies, blood transfusions and IVC filter placement. Once the subject is stabilized, if anticoagulant therapy is considered a clinical option, the subject will be started on apixaban per protocol.

Discontinuation of Apixaban

If a subject must be discontinued from apixaban before the end of the study, this will not result in automatic withdrawal of the subject from the study, and the subject should continue to be followed for efficacy and safety outcomes.

A subject should be discontinued from apixaban if:

- The investigator believes that for safety reasons (ie, adverse event) it is in the best interest of the subject to stop apixaban.
- The subject develops any condition which requires anticoagulation or thromboprophylaxis (ie, atrial fibrillation, VTE).
- The subject becomes pregnant.
- The subject requests to discontinue apixaban permanently
- The subject has a major life-threatening bleed (per GUSTO criteria);

If the subject permanently discontinues apixaban before the 6-month visit, he/she should be instructed to complete an unscheduled visit and the remaining scheduled visits. The investigator will provide a narrative to describe any adverse events that occur up to apixaban discontinuation. The appropriate adverse event or serious adverse event sections of the eCRF are to be completed.

A subject should have apixaban administration interrupted if the following conditions occur:

- Bleeding that is significant that does not fit GUSTO criteria
- Alanine transaminase (ALT) or aspartate transaminase (AST) ≥ 2 times upper limit of normal (ULN)
- Total bilirubin (TBL) ≥ 1.5 times ULN (except due to confirmed Gilbert's syndrome)
- Subjects with a significant drop in hemoglobin

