- Within 24 ± 8 hours of discontinuing treatment, the subject will be assessed for improvement in PE signs and symptoms including sPESI score, repeat CT angiogram for determination of thrombus burden as measured by a Refined Modified Miller Score and RV/LV ratio, and an echocardiogram.
- Laboratory tests for Hgb, Hct, platelet count, aPTT, PT and INR, BNP, troponin, BUN and creatinine will also be obtained.
- Adverse events, VTE recurrence, and bleeding events will be recorded.

Day 2 Assessments

- Vital signs including temperature, respiratory rate, heart rate, blood pressure, and oximetry will be obtained.
- Laboratory tests for Hgb, Hct, platelet count, aPTT, PT and INR, BUN and creatinine will also be obtained.
- Adverse events, VTE recurrence, and bleeding events will be recorded.

Follow-up Clinic Visits and Subject Contact

- The subjects will be followed until Day 365 ± 15 days.
- A 72-hour follow-up assessment of Adverse Events will be conducted either in-person if the subject is still admitted at CSMC, or via telephone call if the subject is discharged.
- A Day 7 follow-up assessment of Adverse Events will be conducted via telephone call.
- The subject will return to the clinic Day 30, 180 and 365.
- The following assessments will be performed at follow-up clinic visits:
 - Echocardiogram at Day 30 and Day 180. Echocardiogram will be repeated at Day 365/EOT if last echocardiogram was abnormal.
 - Blood draw for laboratory tests, including hemoglobin, hematocrit, platelet count, BUN, creatinine, and liver function tests at Day 30.
 Physical exam and vital signs including respiratory rate, heart rate, blood pressure, temperature, and sPO2
 - o 6MWT with Borg score and requirement for oxygen therapy
 - Quality of life (QOL) as measured by the PROMIS PF-6 and Pulmonary Embolism Quality of Life (PEmb-QOL)
 - Adverse Events through 1 year follow-up.
 - Signs or symptoms of recurrent VTE
 - Changes in anticoagulant medications
 - Evidence of chronic thromboembolic disease or chronic thromboembolic pulmonary hypertension
- Phone calls for remote health checks will be conducted at Day 7, Day 90 ± 15 days and Day 270 ± 15 days.

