6.3.2. HARMS

A rigorous screening process will be utilized to verify eligibility. This will include reviewing the imaging diagnosis of PE (to ensure that subjects without acute PE are not inadvertently enrolled in the study), performing a detailed history and physical examination (to ensure that enrolled subjects truly fulfill all eligibility criteria), and carefully reviewing the results of laboratory testing (in particular, hematocrit, platelet count, INR, and creatinine clearance).

During study drug treatment period, the subject will be monitored during the infusion and the infusion will be stopped if bleeding occurs. To reduce the risks associated with the CTA, we will ascertain that the subject has no history of allergic reaction to the contrast and we will make sure their creatinine clearance is adequate.

During the follow-up period, changes in health status will be evaluated by the study doctor and reported as deemed appropriate.

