- Statistical Analysis: We will also compare the RMMS at 24 hours for treatment A, with that of treatment B (saline placebo + IV unfractionated heparin) as a secondary outcome. Data will be analyzed and presented in the same way as the primary outcome.
- Sample Size Justification: Statistical power was estimated in the same way as the primary outcome.
 17 patients per group achieve 91% power to detect a difference of 15 percentage units between 24 hour post-treatment CTAs of treatments A and B.

Another *secondary outcome* is change from baseline RV/LV ratio by chest CTA expressed as percentage change from baseline.

- Statistical Analysis: Statistical analysis for the seconday outcome will be similar to the primary outcome.
- Sample Size Justification: Statistical power was estimated with a two-sided two-sample equalvariance t-test. A previous study [22] showed that the mean and standard deviation of percentage change in RV/LV ratio from baseline to 48 hours are 26 and 22.7, respectively. Assuming these hold for our study , data from 17 patients per group (34 total) achieve 90% power to detect a mean difference of 26 percentage units between the two treatments with 5% significance level using a two-sided two-sample equal-variance t-test.

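### The only analysis-type set in the plan requires a completed infusion, and Section 7 does not say whether it governs the randomised efficacy comparisons

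*Combined protocol and SAP*

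**What the plan says.** The Sample Size row of the synopsis sets two conditions for an evaluable subject, joined by a plain 'and': valid CTAs at baseline and at 24 ± 8 hours after the infusion ends, and that the subject "successfully completed administration of study drug infusion". The sentence after it says that randomised subjects who stop the infusion early because of adverse events are still followed for safety, to Day 30. It says nothing about their efficacy data. The same row, and Section 3.2, add: "Additional subjects may be consented to compensate for screening failures and/or treated patients who lack sufficient data". Neither says whether the subjects being compensated for stay in the analysis.

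The synopsis refers the reader to Section 7 for the statistical analysis. Section 7.1 gives the model, the tests, the power and an attrition allowance from 17 to 20 per arm. It names no intention-to-treat, modified intention-to-treat, per-protocol, evaluable or safety set.

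The rules for stopping the infusion rest on adverse events. Section 3.5: "If a subject develops the following adverse events the alteplase infusion will be permanently discontinued", followed by a list that includes related serious events, new neurological symptoms, severe headache and life-threatening bleeding. Section 6.3.2: "the infusion will be stopped if bleeding occurs".

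The between-arm comparison is a secondary endpoint. Section 1.2.2 lists the RMMS change "from baseline to 24 hours for treatment A compared with treatment B", and Section 7.1.1 says "We will also compare the RMMS at 24 hours for treatment A, with that of treatment B". RV/LV ratio by CTA is compared in the same way. The primary endpoint in Section 1.2.1 is a change within arm A, "after 24 mg of systemic (intravenous; IV) tPA compared with baseline CTA RMMS".

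**The concern.** Infusion completion is observed after randomisation, and it can depend on treatment: tPA can cause the bleeding that stops an infusion, whereas saline does not. If efficacy is analysed only in completers, the A and B groups being compared are no longer the groups that were randomised, and subjects may be lost mainly from one arm. The affected comparisons are the randomised ones, RMMS and RV/LV for A versus B.

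The data for these subjects need not be missing. Section 3.5 keeps a subject with a stopped infusion in follow-up, and Section 5.4.1 schedules the scan relative to the end of treatment ("hours of discontinuing treatment, the subject will be assessed for improvement in PE signs and symptoms including sPESI score, repeat CT angiogram"). A subject can therefore have both CTAs and still fail the evaluable definition.

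With about 20 subjects per arm, one or two exclusions are visible in the result, so the set should be fixed in the plan and not chosen at analysis.

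**Working it through.** **Step 1. What the text settles.**
- Two conditions joined by 'and': both scans plus an incomplete infusion means not evaluable.
- No sentence links evaluable to the Section 7 model, which needs only baseline RMMS, 24-hour RMMS and treatment group.
- Two features point towards efficacy use: the CTA criteria are those of the efficacy endpoints, and the next sentence mentions non-completers only for safety.

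**Step 2. Reproduce the plan's figures, to confirm its SDs** (noncentral t, two-sided 5%, 17 per arm, Section 7.1.1).
- RMMS, A versus B: difference 0.15 × 21.14 = 3.171, SD 2.7. Noncentrality 3.171 / (2.7 × √(2/17)) = 3.42 on 32 df; power 91.3% (plan: 91%).
- RV/LV: difference 26, SD 22.7. Noncentrality 26 / (22.7 × √(2/17)) = 3.34; power 89.9% (plan: 90%).

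**Step 3. Standard errors at 20 per arm.**
- RMMS SD as a percentage of mean baseline: 2.7 / 21.14 = 12.77 points.
- Within arm A: 12.77 / √20 = 2.86.
- A minus B: 12.77 × √(2/20) = 4.04.
- RV/LV, A minus B: 22.7 × √(2/20) = 7.18.

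**Step 4. Shift from excluding one tPA subject.** Assume the 19 completers average 15% lysis, the excluded subject has lysis L, and nobody is excluded in arm B. The mean over all 20 is (15 × 19 + L) / 20, and the shift is 15 minus that mean.

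| L | Mean of all 20 | Shift (points) |
|---|---|---|
| 0 | 14.25 | +0.75 |
| 7.5 | 14.625 | +0.375 |
| 15 | 15.00 | 0 |
| 30 | 15.75 | −0.75 |

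For L = 0: 0.75 / 4.04 = 0.19 SE for A versus B, and 0.75 / 2.86 = 0.26 SE within arm A. For RV/LV with zero change in the excluded subject: 26 / 20 = 1.3 points, and 1.3 / 7.18 = 0.18 SE. With three exclusions at L = 0, the RMMS shift is 15 − (15 × 17) / 20 = 2.25 points.

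**Step 5. How often it could happen.** The documents give no early-stop rate. Section 5.4 gives a 1-minute bolus and a 19-minute infusion. The chance of at least one stop among 20 tPA subjects is 1 − (1 − p)^20:
- p = 1%: 18%
- p = 2%: 33%
- p = 5%: 64%

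**Step 6. Power is not the issue.** With 20 per arm, power for RMMS A versus B is 95.1%. Dropping 1, 2 or 3 subjects from arm A leaves 94.6%, 94.0% or 93.3%.

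**Step 7. Follow-up of non-completers.** The synopsis follows them for safety to Day 30; Section 3.5 follows subjects whose alteplase was stopped until the study ends. Section 1.2.3 has severe or life-threatening bleeding at Days 180 and 365, and death and recurrent PE at Day 365. Both follow-up rules cannot hold for those endpoints.

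**The case against.** The strongest reply is that nothing in the documents restricts efficacy to evaluable subjects. The definition sits in the Sample Size row, beside the sentence on additional subjects, and may serve only to count subjects towards the 17 per arm needed. That stands as a possible reading, and it is why the point is conditional. It does not remove the gap, because under it the plan has no efficacy set at all.

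Other parts of the reply also stand:
- For the within-arm primary, the endpoint's reference to the 24 mg dose makes a completer set defensible. That argument does not carry over to A versus B.
- The reference in Section 5.4.1 to discontinuing treatment is in the routine Day 1 list and probably just means the end of the infusion. It shows that a stopped subject can have the scan, not that the scan is likely after a serious bleed.
- The SE multiples are illustrative: 12.77 is the SD of the absolute change divided by the mean baseline, and the planned analysis is a baseline-adjusted model of the score.
- Section 7.1.2 expects bleeding of 5% or less by Day 30, so a 5% stop rate within 20 minutes looks high for bleeding alone. The other triggers are not quantified.
- Section 6.2.1 has the core laboratory read images in bulk at study end, and Section 4.3 blinds all study personnel except pharmacy. This limits a choice of set driven by results, but not selection by tolerability.

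A reader might infer that the plan already excludes non-completers, or that the lysis result will be inflated. Neither follows: the first is not stated, and the sign of the shift depends on the excluded subjects' lysis, which the documents do not give.

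**Conclusion.** The point holds in conditional form. The one set defined requires a completed infusion, and Section 7 neither adopts nor replaces it. If it governs efficacy, the randomised RMMS and RV/LV comparisons are conditioned on a post-randomisation event that tPA can cause.

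The expected effect is small: about 0.19 SE for RMMS and 0.18 SE for RV/LV per zero-response exclusion, on assumed stop rates, with a direction that cannot be derived. It is worth settling because the change is cheap, not because the result is in serious doubt.

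The Day 30 versus end-of-study difference for non-completers is a separate, actual contradiction. A reader might also count the lack of rules for death, rescue treatment or a missing 24-hour CTA as part of this error. Those are separate open details, and handling them by sensitivity analysis is optional.

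**What to change.** In Section 7:
1. Analyse the A-versus-B RMMS and RV/LV comparisons in all randomised subjects who started study drug, as randomised, with valid baseline and 24-hour CTAs, without requiring infusion completion.
2. State that originally treated subjects stay in the analysis if others are added.
3. Report the completer set as a sensitivity analysis for A versus B. For the within-arm primary, report both sets.

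This set still depends on having a 24-hour CTA, so it removes the completion condition but not every post-randomisation condition. Optional sensitivity analyses could cover death, rescue treatment or a missing scan before 24 hours.

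Separately, reconcile the synopsis with Section 3.5 on how long non-completers are followed for safety, so that the Day 180 and Day 365 safety endpoints have a clear denominator.

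Cost: protocol wording and one extra run of each analysis, with no new visits or scans. The downside is that the lysis estimate may be slightly smaller because partial-dose subjects are included, and the main A-versus-B result no longer describes only subjects who received the full dose.
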